## 1. PROTOCOL SUMMARY

Title:	A Prospective, Multi-Center, Single-Arm, Real World Study Assessing the Clinical Use of the Caterpillar™ Arterial Embolization Device for Arterial Embolization in the Peripheral Vasculature
Sponsor:	Bard Peripheral Vascular, Inc. [name]
Objectives:	The primary objective of this study is to evaluate the performance and safety of the Caterpillar™ Arterial Embolization Device when used for arterial embolization in the peripheral vasculature in a real world, on-label application.
Design:	The post-market study is a prospective, multi-center, single-arm, real world study of the Caterpillar™ Arterial Embolization Device. Follow-up for all treated subjects will be performed at 30 days, as well as 6 and 12 months post-Index Procedure.
Study Device:	
The Caterpillar™ Arterial Embolization Device (Caterpillar™ Micro and Caterpillar™) is a self-expanding arterial occlusion plug, intended for arterial embolization in the peripheral vasculature. The device is intended to be a permanent implant and consists of the following components: a cobalt-chrome stem, nickel-titanium fibers, platinum-iridium radiopaque marker bands and a polyurethane and polyethylene occlusion membrane.
 
The Caterpillar™ Arterial Embolization Device is packaged as a single unit with the implant, loader, dispenser hoop, detachable delivery wire and torque tool. The device is intended for single-use only within a specific arterial vessel size range and does not require oversizing. The available sizes, product characteristics, intended arterial vessel diameter range and required delivery catheter size (inner diameter (ID)) are provided in the Instructions for Use (IFU).

Enrollment:	Enrollment will continue until up to fifty (50) subjects have been treated with the Caterpillar™ Arterial Embolization Device.
Study Sites:	Up to 20 investigational sites in the United States.
Study Population:	Male or non-pregnant female subjects ≥18 years of age who require arterial embolization in the peripheral vasculature.
Primary Endpoints:	
Primary Performance Endpoint:
 
Technical Success
 
Successful occlusion of the target embolization site(s) as confirmed by the Investigator via angiographic assessment during the Index Procedure. Technical success will be reported for each target embolization site.
 
Primary Safety Endpoint:
 
Freedom from Device-Related Serious Adverse Events (SAE)
 
Freedom from device-related serious adverse events (SAE) through 30-day follow-up.

Secondary Endpoints:	
Time Point of Occlusion The percentage of target embolization site(s) with occlusion at ≤1, ≤2, ≤3, ≤4, ≤5, ≤10 and >10 minutes post-treatment.
 
Freedom from Recanalization Freedom from clinically relevant recanalization of the target embolization site(s) through 30-days, 6 and 12-months follow-up as confirmed by the Investigator. Clinically relevant recanalization is defined as recanalization through the study device that requires a re-intervention. Freedom from recanalization will be reported for each target embolization site.
 
Freedom from Migration Freedom from Migration will be reported for each study device as follows:
 

• Freedom from clinically relevant acute migration of the study device(s) as confirmed by the Investigator via angiographic assessment during the Index Procedure. Clinically relevant migration is defined as migration of the study device from the target embolization site that requires intervention.

• Freedom from clinically relevant migration of the study device(s) through 30-days, 6 and 12-months follow-up as confirmed by the Investigator. Clinically relevant migration is defined as migration of the study device from the target embolization site that requires a re-intervention.

 
Freedom from Device and/or Procedure-Related Adverse Events Freedom from device and/or procedure-related adverse events (AE) through 30-days, 6 and 12-months follow-up.
 
Accuracy of Delivery Accurate delivery of the study device to the target embolization site as assessed by the Investigator.
 
Ease of Trackability/Deliverability Ease of study device trackability and deliverability as assessed by the Investigator.
 
Ease of Detachment Ease of study device detachment as assessed by the Investigator.
 
Acceptability of Visibility Acceptability of study device visibility under fluoroscopy as assessed by the Investigator.

-----------------------------	---

Inclusion Criteria:	
Clinical Inclusion Criteria
 

1. Subject or Legally Authorized Representative (LAR) must voluntarily sign and date the approved Informed Consent Form (ICF) prior to collection of study-specific data or performance of study-specific procedures.

2. Subject must be either male or non-pregnant female <math>\geq 18</math> years of age with an expected lifespan sufficient to allow for collection of primary endpoint data.

3. Subject must be willing and able to comply with protocol requirements, including all study visits and procedures.

4. Subject must require peripheral vascular occlusion at an arterial target embolization site(s) that can be treated with the Caterpillar™ Arterial Embolization Device according to the Instructions for Use (IFU). Note: Per Investigator discretion, up to five (5) Target Embolization Sites may be treated with up to ten (10) study devices per subject.

 
Angiographic Inclusion Criteria
 

5. The target embolization site(s) must be located in a native arterial vessel(s) with the intended arterial vessel diameter ranges shown in the IFU, as assessed by the Investigator (via visual estimate).

6. The target embolization site(s) must have a landing zone sufficient to accommodate the device implant lengths shown in the IFU.

Exclusion Criteria:	
Clinical Exclusion Criteria
 

1. The subject's access vessel(s) preclude safe insertion of the delivery catheter.

2. The subject's target embolization site(s) is located within a vein.

3. The subject's target embolization site(s) is located within the head, neck, heart or coronary vessels.

4. The subject's target embolization site(s) is located across highly locomotive joints or muscle beds (e.g. elbow, hip, knee, shoulder, thoracic inlet/outlet).

5. The subject's target embolization site(s) is located in a high-flow vessel where, in the opinion of the Investigator, there may be significant risk of migration and unintended (non-target site) occlusion.

6. The subject has a known allergy or hypersensitivity to contrast media that cannot be adequately pre-medicated.

7. The subject has a known allergy or hypersensitivity to any of the device materials including: cobalt, chromium, nickel, titanium, platinum, iridium, polyurethane or polyethylene.

8. The subject has planned use of anticoagulant (e.g. direct thrombin inhibitors, factor Xa inhibitors, vitamin K antagonists) or antiplatelet therapy before, during and/or after treatment with the study device,

	
which, in the opinion of the Investigator, would clinically interfere with the study endpoints.
 
9. The subject has a known uncontrolled blood coagulation or bleeding disorder.
 
10. The subject has an unresolved systemic infection.
 
11. The subject's required pre-operative laboratory tests and/or physical examination indicate abnormal results, which, in the opinion of the Investigator, would clinically interfere with the study endpoints.
 
12. The subject has a connective tissue disorders (e.g. Ehlers-Danlos Syndrome), arteritis (e.g. Takayasu's Disease) or another circulatory disorder, which, in the opinion of the Investigator, would clinically interfere with the study endpoints.
 
13. The subject has another medical condition which, in the opinion of the Investigator, may cause him/her to be non-compliant with the protocol, may confound the data interpretation, or is associated with a life expectancy insufficient to allow for the collection of primary endpoint data.
 
14. The subject is currently participating in an investigational drug or another device study that has not completed the study treatment or that clinically interferes with the study endpoints. Note: Studies requiring extended follow-up visits for products that were investigational, but have since become commercially available, are not considered investigational studies.

Procedures:	All subjects will undergo an in-office clinical evaluation at the Screening Visit (prior to Index Procedure). Subjects that meet Eligibility Criteria will undergo additional in-office clinical evaluations and will be treated with the Caterpillar™ Arterial Embolization Device at the Index Procedure visit. An in-office follow-up visit or telephone contact will be performed at 30 days, as well as 6 and 12 months post-Index Procedure for all treated subjects.
Principal Investigator:	[name], FSIR Medical College of Wisconsin Division of Vascular and Interventional Radiology [name]
Medical Monitor:	[name], FSIR Vanderbilt University Medical Center Department of Radiology [name]

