## **2. STATISTICAL METHODS**

This section describes the planned statistical analyses for the study. A detailed Statistical Analysis Plan (SAP) will be developed that outlines the methodology used in the statistical analyses described below.

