### **2.3. Data Analysis**

The analysis population consists of all subjects who have been treated with the study device as defined in Section 5.2.3.

Data collected in this study will be summarized using descriptive statistics. Summary statistics will include frequency counts and percentages for categorical variables and mean, standard deviation, minimum, median, and maximum for continuous variables.

- Reduced number of embolization devices required per procedure, potentially resulting in reduced procedural time and fluoroscopy exposure

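### Does reporting Technical Success by embolization site, with no subject-level figure in the available text, leave the primary performance result unsound?

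*Combined protocol and SAP*

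**What the plan says.** The primary performance endpoint in the Protocol Summary is investigator-confirmed angiographic occlusion during the index procedure, and the reporting unit is explicit: "Technical success will be reported for each target embolization site". Inclusion criterion 4 allows several sites per subject: "Per Investigator discretion, up to five (5) Target Embolization Sites may be treated with up to ten (10) study devices per subject".

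The secondary endpoints also name their units. Time to occlusion is "The percentage of target embolization site(s) with occlusion at" a series of cut-points in minutes. For the later endpoints, "Freedom from recanalization will be reported for each target embolization site" and "Freedom from Migration will be reported for each study device as follows".

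Section 2.3 defines the population by subject ("The analysis population consists of all subjects who have been treated with the study device") and the method as descriptive: "Summary statistics will include frequency counts and percentages for categorical variables". Section 2.1 states that there is no formal hypothesis, and Section 2.2 that the sample size has no statistical basis. Section 2 leaves the detail to a later document: "A detailed Statistical Analysis Plan (SAP) will be developed that outlines the methodology". The content of that SAP, and Section 5.2.3 on which the population definition relies, are not in the text available here.

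**The concern.** The analysis population is counted in subjects and the primary performance result in sites. The number of sites per subject is left to the investigator, so a subject with five sites carries five times the weight of a subject with one. The available text has no line for subjects with all treated sites occluded, and no table of sites per subject.

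A clinician may read the site percentage as the share of patients treated successfully. It need not be. If the failures gather in one subject, the share of patients fully treated is higher than the site rate; if they are spread over several subjects, it can be lower. With no hypothesis test, the descriptive percentage is the main performance result, so its meaning matters.

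**Working it through.** The plan states no figure to reproduce. The check asks how far a site rate and a subject rate can differ, and whether the plan already defines its own summary.

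**Inputs.** From the documents: up to 50 treated subjects (Protocol Summary, Enrollment) and at most five sites each (inclusion criterion 4). Assumed: the mix of sites per subject and the number of failed sites.

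**Is the planned summary defined?** The endpoint fixes the site as the unit, Section 2.3 calls for counts and percentages, and the time-to-occlusion endpoint is already a percentage of sites. Read together, they give occluded sites divided by treated sites. What is absent is a second summary, not the rule for the planned one.

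**Bounds.** Take k subjects with five sites and 50 − k with one, so N = 50 + 4k sites, with five failed sites.

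- k = 5: N = 70, and the site rate is 65/70 = 92.9%.
- All five failures in one five-site subject: 49/50 = 98.0% of subjects fully occluded.
- Five failures in five different subjects: 45/50 = 90.0%.
- k = 1: site rate 49/54 = 90.7%. k = 10: site rate 85/90 = 94.4%. The subject bounds stay at 98.0% and 90.0%, because five failures and at least one five-site subject are assumed each time.

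The 8-point spread therefore compares two extremes. The upper one requires every site of a single subject to fail and no other site in the study to fail.

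**Failures at random.** A one-site subject succeeds with probability (N − 5)/N. A five-site subject has all sites occluded with probability C(N − 5, 5)/C(N, 5). The expected number of fully occluded subjects is

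(50 − k)(N − 5)/N + k·C(N − 5, 5)/C(N, 5).

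| k | N | Site rate | Expected subjects | Subject rate | Gap (points) |
|---|---|---|---|---|---|
| 1 | 54 | 90.7% | 44.46 + 0.60 = 45.07 | 90.1% | 0.6 |
| 5 | 70 | 92.9% | 41.79 + 3.41 = 45.20 | 90.4% | 2.5 |
| 10 | 90 | 94.4% | 37.78 + 7.46 = 45.24 | 90.5% | 4.0 |

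**The permitted maximum.** If all 50 subjects had five sites (250 sites) and 225/250 = 90% were occluded, the 25 failures could fall in 25 different subjects (25/50 = 50% fully occluded) or in five (45/50 = 90%). With independent sites the expectation is 50 × 0.9^5 = 29.5 subjects, or 59%. At 245/250 = 98% the range is 45 to 49 subjects, with 50 × 0.98^5 = 45.2 expected. At the other end, if every subject has one site, the two rates are identical.

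**Precision.** Clustering of sites within subjects would matter to an interval or test on the site rate. For the 70-site mix the design effect is 1 + (170/70 − 1) × ICC, which is 1.14 at an assumed ICC of 0.1 and 1.71 at 0.5. The available text plans no interval or test, so this inflates nothing in the plan.

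**The case for a change.** The best case for a change is that the addition costs a few lines of SAP text and code, needs no new data, and removes a possible misreading of the main performance figure. If multi-site treatment is common, the misreading could be large: at the permitted maximum, 90% of sites could go with as few as half of the patients fully occluded. The documents give only the maximum number of sites, so a heavily multi-site sample cannot be excluded.

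All of that stands as a reason to report more; it does not show the planned result to be wrong. The site is a deliberate choice of unit that suits the first part of the stated objective, the performance of the device. The primary safety endpoint carries no per-site or per-device rule, so it is plausibly a subject-level result already. A subject-level count and a table of sites and devices are ordinary contents of the SAP that Section 2 promises, and the text available here cannot show that they are missing from it. If they are, the same data yield them at any time, so nothing is lost by leaving the protocol as it is. Clustered intervals, by generalized estimating equations or a bootstrap, would answer a question that the plan does not ask.

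**Conclusion.** No change to the plan is needed. Followed as written, it gives a sound descriptive site-level rate, and no hypothesis, performance goal or interval in the available text depends on a subject-level figure. The observation itself is correct: the site rate does not tell a reader how many subjects had every treated site occluded. The gap is zero with one site per subject. With five failures at random it is about 0.6 to 4.0 points for one to ten five-site subjects among 50, and it is much larger only if most subjects have several sites and failures are not rare. These sizes rest on assumed mixes and failure counts. The matter is a gap in reporting detail that the SAP authors can fill sensibly, by giving the number of subjects with all treated sites occluded and tabulating sites and devices per subject, if they find it useful.

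### Can index-procedure failures count as free of migration or recanalization at 12 months, and does the plan need changing for it?

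*Combined protocol and SAP*

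**What the plan says.** All the relevant endpoints are in Section 1 (Protocol Summary).

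- **Migration, unit:** "Freedom from Migration will be reported for each study device as follows". Two bullets follow.
- **Acute migration**, judged by angiography during the Index Procedure: "Clinically relevant migration is defined as migration of the study device from the target embolization site that requires intervention".
- **Migration through 30 days, 6 and 12 months:** "Clinically relevant migration is defined as migration of the study device from the target embolization site that requires a re-intervention".
- **Recanalization** counts only if it is through the study device and needs a re-intervention. On the unit: "Freedom from recanalization will be reported for each target embolization site".
- **Initial occlusion** is the primary performance endpoint, in the same unit: "Technical success will be reported for each target embolization site".

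Section 2.3 gives one population, "The analysis population consists of all subjects who have been treated with the study device as defined in Section 5.2.3", and a descriptive method: "Summary statistics will include frequency counts and percentages for categorical variables". Section 5.2.3 is not in the text available for review. Section 2 leaves the detail to a later document: "A detailed Statistical Analysis Plan (SAP) will be developed that outlines the methodology used in the statistical analyses described below". Section 2.1 states that there is no formal hypothesis, and Section 2.2 that the sample size has no statistical basis.

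**The concern.** The two migration bullets differ by one word, and that word defines the event. A device that moves and is corrected or retrieved during the Index Procedure has had an intervention, but not necessarily a re-intervention. It fails the acute endpoint and may still pass the 12-month one. The text does not say that acute events carry forward.

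Recanalization has a similar gap. A site that never occluded cannot reopen. If it stays in the denominator, it counts as a success on an endpoint for which it was never at risk.

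What is at stake is interpretation. A reader may take freedom from migration through 12 months as cumulative from implantation, and freedom from recanalization as describing occlusions that were achieved. Neither is guaranteed by the wording. The 12-month migration figure could even exceed the acute figure in the same table, which a cumulative freedom rate cannot do.

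**Working it through.** The plan states no rate, margin or power for these endpoints, so there is no figure to reproduce. The check is to compute the candidate readings and see how far apart they lie.

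**Inputs.** From the documents (Section 1): up to 50 treated subjects, up to 5 sites and 10 devices each, so at most 50 × 5 = 250 sites and 50 × 10 = 500 devices. Assumed: an index-failure rate f and a later-event rate r among units at risk, each from 2% to 10%, with no loss to follow-up and no later event in a unit that failed at index.

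**Formulas.**

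- Literal (index failures kept and counted as free): 1 − (1 − f)r
- At-risk (index failures excluded): 1 − r
- Cumulative or composite (index failures counted as failures): (1 − f)(1 − r)

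Literal minus at-risk is f × r. Literal minus cumulative is f.

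**Results.**

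| f | r | Literal | At-risk | Cumulative | Literal − at-risk | Literal − cumulative |
|---|---|---|---|---|---|---|
| 2% | 2% | 98.04% | 98.0% | 96.04% | 0.04 points | 2 points |
| 5% | 5% | 95.25% | 95.0% | 90.25% | 0.25 points | 5 points |
| 10% | 10% | 91.0% | 90.0% | 81.0% | 1.0 point | 10 points |

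**Worked counts (assumed).**

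- *Migration, 50 devices, 2 acute and 1 later on a different device.* Acute freedom 48/50 = 96.0%. Through 12 months: literal 49/50 = 98.0%, at-risk 47/48 = 97.9%, cumulative 47/50 = 94.0%. Exact 95% intervals are 89.4% to 99.9% for 49/50 and 83.5% to 98.7% for 47/50.
- *Recanalization, 50 sites, 3 never occluded and 2 recanalized.* Literal 48/50 = 96.0%, at-risk 45/47 = 95.7%, composite 45/50 = 90.0%.

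**Can a reader recover the cumulative figure?** Section 2.3 promises counts as well as percentages. In the migration example, 2 acute and 1 later event over 50 devices mean 2 or 3 devices affected, depending on whether the later event is on a device already counted. Cumulative freedom is then 48/50 = 96.0% or 47/50 = 94.0%. The separate lines bound the answer to within one device.

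**Step size.** One index failure moves the cumulative figure by 1/50 = 2.0 points with one unit per subject, by 1/250 = 0.4 points at the site cap, and by 1/500 = 0.2 points at the device cap.

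**The case for a change.** The best case for a change is that the time window and the event definition do different work. Even if the follow-up window opens at implantation, the narrower event can still leave out a migration corrected on the table. The adverse-event endpoint uses the same follow-up times without narrowing its event, so the narrowing for migration has an effect. The device is a permanent implant, and migration and recanalization are the only listed performance endpoints that run past the procedure. One sentence fixed in advance would remove a choice that might otherwise be made after the results are seen.

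Part of this stands. The wording does not settle the matter, and separate percentages without their denominators would not let a reader rebuild a cumulative rate.

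The rest is weaker:

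- Counting index failures as free is one permitted reading, not a stated rule. Follow-up is timed from the Index Procedure, so a cumulative reading is just as natural. The available text does not define re-intervention.
- Reporting acute and later migration separately is a defensible choice. They are different clinical events, and a higher 12-month figure beside a lower acute one is then not a contradiction.
- The plan never claims to measure sustained occlusion. A line combining technical success with no clinically relevant recanalization would be an added endpoint. It would still miss a site that reopened silently, because the event needs a re-intervention and follow-up may be by telephone.
- The gap formulas assume that an index failure has no later event. A device repositioned and left in place could migrate again, and a site still open at the end of the procedure could occlude later and then reopen.

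**Conclusion.** The ambiguity is genuine but minor, and the plan gives sound descriptive results as it stands. Against the endpoints as defined, the only distortion is in the denominator. It is f × r, or 0.04 to 1.0 percentage point for assumed rates of 2% to 10%. That is small beside the sampling uncertainty: with 49 of 50 free, the exact 95% interval spans about 10 points.

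The 2 to 10 point gap is the assumed index-failure rate itself, seen only when the result is set against a cumulative or composite measure that the plan does not promise. That rate is already visible, as the primary performance endpoint per site and as acute migration per device. No hypothesis, threshold or decision depends on the follow-up figures.

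What remains is ordinary SAP detail: when the migration window starts, whether acute events carry forward, which sites form the recanalization denominator, and n/N on each line. Analysts would be expected to settle these when writing the SAP, and Section 5.2.3 or the SAP may already do so. Neither could be checked here. The conclusion rests on acute migration and technical success being reported beside the follow-up results, as Section 1 provides.

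### Do the four device-handling endpoints need a stated reporting unit before their percentages mean anything?

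*Combined protocol and SAP*

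**What the plan says.** The secondary endpoints in Section 1 (Protocol Summary) end with four investigator ratings of how the device handles. The one on accuracy is worded "Accurate delivery of the study device to the target embolization site as assessed by the Investigator". The rating for detachment is given as "Ease of study device detachment as assessed by the Investigator", and those for trackability and for fluoroscopic visibility follow the same pattern.

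None of these carries a statement of the reporting unit. Four other endpoints do. For the primary performance endpoint, "Technical success will be reported for each target embolization site". Time Point of Occlusion is defined as a percentage of sites, and freedom from recanalization is also reported site by site. For migration, "Freedom from Migration will be reported for each study device as follows".

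Inclusion criterion 4 allows several units in one subject: "up to five (5) Target Embolization Sites may be treated with up to ten (10) study devices per subject". Section 2.3 states that "The analysis population consists of all subjects who have been treated with the study device", and plans counts with percentages for categorical data and the usual summaries for continuous data. Sections 2.1 and 2.2 say that there is no formal hypothesis and that the sample size has no statistical basis. Section 2 announces a separate, detailed SAP.

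**The concern.** The authors stated a unit for four endpoints where one subject can contribute several sites or devices, and left it out for four others. Migration is also about the device, yet there the unit is spelled out, so the silence on handling could be read as leaving the matter open. Accuracy of Delivery mentions both device and site. If Section 2.3 is taken to set a subject denominator, some rule is needed to reduce several device ratings to one per subject, and none is given.

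The stake would be reproducibility. Two analysts with the same ratings could report different percentages, and in a study with no hypothesis the descriptive percentages are the result.

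**Working it through.** There is no planned figure to reproduce, since the sample size is not derived from statistical inputs. The check has three parts.

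**1. Units, side by side (Section 1)**

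| Endpoint | Unit stated? | Unit |
|---|---|---|
| Technical success | yes | site |
| Time point of occlusion | yes | site |
| Freedom from recanalization | yes | site |
| Freedom from migration | yes | device |
| Device-related SAEs (primary safety) | no | subject, from the sense |
| Device/procedure-related AEs | no | subject, from the sense |
| Four handling endpoints | no | device, from the sense |

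An omitted unit sentence is therefore not in itself a defect in this plan. The two adverse-event endpoints omit it as well, and nobody would misread them. All seven rows are analysed in the same population of treated subjects under Section 2.3, although three are explicitly per site and one per device. That section thus cannot be what fixes the denominator. What remains is the endpoint wording, and each of the four speaks of the study device. Section 1 describes the device as a single-use unit packaged individually with its own delivery wire, so tracking and detachment happen one device at a time.

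**2. How far the denominators could differ**

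Inputs: up to 50 treated subjects (Section 1, Enrollment); up to 5 sites and 10 devices each (inclusion criterion 4).

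- Subjects: 50
- Sites: 50 × 5 = 250
- Devices: 50 × 10 = 500

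The layouts below are assumed, with a favourable/unfavourable rating also assumed. The subject figure counts a subject as favourable only if every device was.

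| Assumed layout | Per device | Per subject | Per device minus per subject |
|---|---|---|---|
| 50 subjects × 1 device, 5 unfavourable | 45/50 = 90.0% | 45/50 = 90.0% | 0 points |
| 45 × 1 and 5 × 3, one unfavourable in each of the 5 | 55/60 = 91.7% | 45/50 = 90.0% | 1.7 points |
| 40 × 1 and 10 × 4, one unfavourable in each of the 10 | 70/80 = 87.5% | 40/50 = 80.0% | 7.5 points |
| 49 × 1 and 1 × 10, five unfavourable in that one | 54/59 = 91.5% | 49/50 = 98.0% | −6.5 points |
| 50 × 10, one unfavourable in each | 450/500 = 90.0% | 0/50 = 0% | 90 points |

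The difference runs from nothing to very large and can take either sign. It is governed entirely by the layout chosen. The supplied text gives neither a distribution of devices per subject nor a rating scale, so no row can be called the expected one. Larger gaps could be produced by other ways of combining ratings within a subject, such as taking the median, but no such rule appears in the plan.

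**3. Could a reader tell which denominator was used?**

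Section 2.3 plans counts together with percentages. In the second row, 55 reported as 91.7% gives 55 / 0.917 = 59.98, so the denominator is 60 devices and not 50 subjects. In the third, 70 / 0.875 = 80. The unit can be recovered from the table itself.

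**The case for a change.** The best argument for a change is that per-device reporting is implied and never written. Migration shows that the authors knew how to write it. An investigator could plausibly give one overall visibility or ease rating for the whole procedure, and the wording would bear that too. Adding a unit to each endpoint would cost four short phrases.

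Part of this stands. The unit is indeed not stated in the text supplied, and writing it down would be tidy. It does not amount to a fault, because the way the ratings are recorded settles the denominator in either case. If each device is rated, the percentages are of devices. If one rating is recorded per subject, they are of subjects, and there are no multiple ratings to combine. A difficulty arises only if an analyst holds device-level ratings and chooses to collapse them to subjects, and nothing in the plan asks for that.

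The case report form, the announced SAP and Section 5.2.3 are not in the supplied text, and any of them may already state the unit. The handling of a device that was attempted but not implanted belongs at the same level of detail.

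**Conclusion.** No change is needed. This is a gap that an analyst would fill sensibly by reporting the four handling ratings per device, in line with the endpoint wording and with the migration endpoint. No stated rule leads to a wrong result, and no test, interval, sample size or success criterion is touched. The numerical effect is zero with one device per subject and otherwise cannot be determined from the documents.

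The conclusion assumes that ratings are recorded either per device or once per subject, and that counts are shown beside percentages as Section 2.3 plans. The per-site unit for technical success and the per-device unit for migration are legitimate choices and raise no issue here.
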